Non-invasive Positive Expiratory Pressure (nPEP) Device for TBM-associated Cough

NCT04169282

Protocol version: 6/13/2019

Non-invasive Positive Expiratory Pressure (nPEP) Device for TBM-associated Cough

Abstract

We aim to determine if an expiratory resistance device that delivers non-invasive positive expiratory pressure (nPEP) will abort coughing paroxysms, reduce airway resistance and improve quality of life in patients with tracheobronchomalacia (TBM) who are not candidates for tracheal stenting.

Research Summary

Patients at Duke University Hospital referred to General Pulmonary and Interventional Pulmonary services for evaluation of severe, debilitating TBM-related cough and possible tracheal stenting, but who are not candidates for tracheal stenting due to their airway anatomy, will be given the nPEP device.

The nPEP device is assembled using mostly existing components with a history of respiratory applications. Specifically, a standard, adjustable (5-20 cm H₂O) positive end expiratory pressure (PEEP) valve manufactured for attachment to a manual resuscitator (commonly known as bag-valve-mask) device is connected to a flexible respiratory mask. Patients will be instructed by the study team as to how to use the nPEP device. The patients will trial the nPEP device immediately during their clinical encounter and will be given a mask to take home for 2 weeks.

Objectives-primary

The primary objective is to determine if use of the nPEP device can decrease cough severity and improve cough related quality of life (QOL).

Objectives-secondary

The secondary objective is to determine if use of the nPEP device improves airway physiology by decreasing proximal airway resistance as assessed by impulse oscillometry.

Objectives & hypothesis

Background and significance- Tracheobronchomalacia (TBM) is a condition in which the cartilage and/or other connective tissue in the trachea and bronchi are weak, resulting in collapse of those large airways during exhalation, especially forceful exhalation as occurs with coughing [1]. The airway collapse with coughing leads to further, ongoing coughing, possibly because mechanical stimulation of the mucosa during collapse may cause localized mucosal inflammation or stimulation of neural circuits that control cough.

TBM can cause a range of symptoms, including debilitating paroxysms of coughing, dyspnea, wheezing, and recurrent respiratory infections. In severe cases of TBM-related cough, patients experience morbidity including QOL impairment, social isolation, fatigue, loss of ability to work, recurrent hospital and even intensive care unit admissions.

The only curative treatment for TBM is a surgical procedure called tracheobronchoplasty, in which the chest is opened and the posterior membrane of the trachea and/or bronchi are surgically affixed to nearby structures, with or without implantation of surgical mesh [2]. This is an approximately 6 hour procedure performed only at specialized centers with appropriate expertise, and only after patients have undergone and proven to benefit from temporary implantation of a tracheal/bronchial stent in the region of collapse. Many patients are not candidates for tracheobronchoplasty itself due to medical comorbidities, prefer to avoid the

associated risks, or are not candidates for the required tracheal stenting due to trachea size or anatomy. These patients are left without a viable therapeutic option for their severe cough.

Continuous positive airway pressure (CPAP) devices have been reported to stop or prevent cough in TBM, presumably through the pneumatic stenting of large airways to maintain their patency during exhalation [3]. CPAP devices, however, are not labeled for this indication and their functional utility is very limited given size of the device, need for a power source, and multiple steps to don the equipment that are not easily completed while actively and uncontrollably coughing. We hypothesize that use of the nPEP device will result in decreased cough severity and improve cough quality of life by decreasing proximal airway resistance as assessed using impulse oscillometry.

Design

Ten subjects with chronic cough and TBM diagnosed by bronchoscopy or computed tomography (CT) scan will be recruited. Comorbid conditions that can cause chronic cough, such as asthma, COPD, and GERD, must be treated if present, for subjects to qualify. At the pre-baseline visit (V-1), after obtaining written informed consent, each subject will complete validated cough questionnaires to quantify their cough severity and cough-related QOL at baseline. The baseline visit (V1) will occur approximately two weeks later, after a run-in period to minimize observation bias related to the cough questionnaires. At V1, the cough questionnaires will be repeated and subjects' airway resistance and reactance will be measured with impulse oscillometry (IOS). Subjects will then be given the nPEP device by the study team and instructed on its use. Approximately two weeks after device delivery, at the follow-up visit (V2), cough questionnaires and IOS will be repeated and they will be asked for feedback regarding device design and user experience. Subjects may then be entered into a cohort for up to six additional months, during which there will be no study visits or procedures, but subjects may be contacted by investigators for additional narrative feedback on the device and its use.

Inclusion and Exclusion Criteria

Inclusion Criteria:

- Age \geq 18 years
- Chronic cough for at least 8 weeks
- Visualization of \geq 50% collapse of the trachea or mainstem bronchus on CT scan or bronchoscopy
- No upper or lower respiratory infection within 4 weeks
- Negative evaluation or treatment response for cough:
 - o Asthma (negative spirometry or treatment with oral corticosteroids or \geq moderate dose of inhaled corticosteroids)
 - o GERD (negative pH probe or treatment with proton pump inhibitor)
 - o Upper airway disease (nasal or oral corticosteroids, antihistamines)
 - o COPD (negative spirometry or treatment with triple-inhaled therapy [\geq moderate dose of inhaled corticosteroids, long-acting muscarinic antagonist, and long-acting beta agonist])
- Having capacity to provide legal written informed consent

Exclusion Criteria:

- History of tracheobronchoplasty or chronic tracheal stenting
- Current tracheostomy
- History of external chest trauma
- History of mediastinal goiter

- Current smoking within 6 months
- Current use of ACE inhibitor within 6 weeks
- Primary parenchymal lung disease
- History of:
 - o Sarcoidosis
 - o Interstitial lung disease
 - o Chronic mycobacterial infection
 - o Lung cancer
 - o Lung transplantation
- Unstable congestive heart failure
- History of spontaneous pneumothorax
- Other medical conditions that interfere with participation in the study

Screening

Potential subjects will be identified through two mechanisms:

1. Potential subjects can be referred to the investigators by their physicians
2. Study staff will identify qualifying subjects within the Duke electronic medical record (EMR) by searching for Duke patients with “tracheobronchomalacia” or its synonyms on their EMR problem list or in the text of a CT scan, discuss potential eligibility with each patient’s physician or provider, and, if appropriate, ask the patient’s physician to contact the patient regarding the study.

Up to 20 patients will be screened to achieve a total of 10 enrolled participants.

Study Interventions

After informed consent is obtained, study subjects will be given an nPEP device to use for two weeks. During this time participants will be asked to remain on their current medical regimen and not to make any dose changes or add new drugs, unless indicated by their primary care provider. Impulse oscillometry will be measured at V1 and 2 weeks later at V2 to assess effect of the nPEP device on airway physiology.

Description of assessments

- a. Medical history: Should include all medically significant events prior to enrollment, including surgical procedures.
- b. Physical exam (PE): Examination of the head, neck, chest, lungs, heart, abdomen, and extremities.
- c. Impulse oscillometry: A noninvasive and rapid technique in which small pressure oscillations are applied through a mouthpiece to measure pulmonary resistance and reactance, which are graphically displayed.
- d. Cough questionnaires: The Cough Specific Quality of Life Questionnaire (CQLQ), Leicester Cough Questionnaire (LCQ), and Cough Visual Analog Scale (Cough-VAS)

Study visits

Pre-baseline visit (V-1, -2 weeks [window -14 to -30 days])

- Review and sign informed consent
- Medical history
- Concomitant medication review
- Physical exam

- Cough questionnaires
 - Cough Specific Quality of Life Questionnaire (CQLQ)
 - Leicester Cough Questionnaire (LCQ)
 - Cough Visual Analog Scale (Cough-VAS)

Baseline visit (V1)

- Update medical history
- Concomitant medication review
- Impulse oscillometry
- Cough questionnaires
 - Cough Specific Quality of Life Questionnaire (CQLQ)
 - Leicester Cough Questionnaire (LCQ)
 - Cough Visual Analog Scale (Cough-VAS)
- Delivery of nPEP device and instruction on its use

Visit 2 (V2, +2 weeks [window +11 to +28 days])

- Update medical history
- Concomitant medication review
- Impulse oscillometry
- Cough questionnaires
 - Cough Specific Quality of Life Questionnaire (CQLQ)
 - Leicester Cough Questionnaire (LCQ)
 - Cough Visual Analog Scale (Cough-VAS)
- Exit interview re: subject experience and preferences regarding device design and use

Cohort for Ongoing Device Feedback

Subjects may be entered into a cohort at the time of study completion, continuing for six months. During this time, no study procedures are planned, but subjects may be contacted and asked to give further opinions regarding any changes in device design and function that may occur after they have completed the study. Each communication or contact that occurs while in this cohort will be voluntary, and subjects may decline or opt out of these communications at any time.

|

	Pre-baseline Visit -1 (V-1) Week -2 window -14 to -30 days	Baseline Visit 1 (V1) Day 0	Follow-up Visit 2 (V2) Week +2 window +11 to +28 days	Unscheduled visit
Consent	X			
Medical History	X			
Interval medical history		X	X	X
Concomitant medication review	X	X	X	X
PE	X			X*
IOS		X	X	
Cough/QOL Questionnaires: CQLQ LCQ C-VAS	X	X	X	X
Device demo and instructions		X		
Adverse event review			X	X
Exit interview			X	X*

*At investigator's discretion

Device Description

The nPEP device is intended as a single-patient, adjustable expiratory resistance device that provides positive pressure (5 to 20 cm H₂O) during expiration. The device is assembled using mostly existing components with a history of respiratory applications. Specifically, a standard, adjustable (5-20 cm H₂O) positive end expiratory pressure (PEEP) valve manufactured for attachment to a manual resuscitator (commonly known as bag-valve-mask) device is connected by a connector piece to a flexible respiratory mask. The connector piece contains a one-way valve to allow for inspiration through the mask. The user may adjust the resistance of the device by rotating the top of the PEEP valve, until the desired effect (cessation of coughing episodes) is obtained.

Fig. 1. nPEP device

Potential Benefits

Subjects may experience direct benefit from the device, including reduction in cough symptom severity and increase in cough-related QOL. There is also a potential scientific and societal benefit in that this pilot study will enhance understanding of whether or not an nPEP device could be further studied in order to present a non-invasive alternative to tracheobronchoplasty for patients with TBM-related cough.

Potential Risks

Potential risks related to participation in this pilot study include risk to privacy, risk of skin irritation from device components, and risk of pneumothorax from positive pressure during cough. Privacy risk will be minimized by securing all personal health information in a locked cabinet or office, entering data into an electronic database protected by the Duke University firewall, and using only de-identified data in data exports. Risk of skin irritation from the device is minimal, given that the mask used is an approved, off-the-shelf component used in other medical applications, and contact dermatitis is a mild condition typically relieved by withdrawal of the offending agent; a literature review has indicated that contact dermatitis is very rare following use of medical facemasks. There is a potential theoretical risk of pneumothorax. The expectation is that this would be a rare occurrence as the pathophysiology of TBM is such that central airway resistance likely prevents the pressure set at the device from being transmitted to the distal small airways or lung parenchyma. The maximum resistance applied by the device (20 cm H₂O) remains very small in comparison to the intrathoracic pressure generated through coughing itself, which has been shown to be in the range of 136-340 cm H₂O [4]. Regardless, patients with personal history of prior pneumothorax or primary parenchymal lung disease will be excluded.

Costs to subject

There will be no additional costs to subjects of the study. Routine care will be charged to the participant or their insurance.

Subject reimbursement

Subjects will be reimbursed a total of \$50 for study completion. This will be issued upon completion of Visit 2.

Data analysis

Statistical analyses include: a) descriptive and summary statistics of demographic and clinical variables, b) pre and post nPEP device treatment comparison of the primary and secondary outcomes (cough quality of life) using paired t-test for normally distributed and transformed data or Wilcoxon's Signed Rank test for non-parametric paired data, and c) pre and post nPEP device assessment of airway physiology as assessed by impulse oscillometry.

Data will be collected on paper forms and stored in each patient's research binder on a secure location. Data will be entered into Redcap for subsequent analysis.

Data and Safety Monitoring

In accordance with federal regulations the PI will monitor for, review, and promptly report to the IRB, appropriate institutional officials, sponsor, coordinating center and the appropriate regulatory agency head all unanticipated problems involving risks to subjects or others that occur in the course of a subject's participation in a research, all AE reports will be reported per the DUHS IRB policies.

Role of external personnel

No external personnel

References

- 4 Sharpey-Schafer EP. Effects of coughing on intrathoracic pressure, arterial pressure and peripheral blood flow. *J Physiol*. 1953 Nov 28;122(2):351-7.

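### The risk section promises to exclude anyone with a prior pneumothorax, but the exclusion list bars only spontaneous pneumothorax

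*Combined protocol and SAP*

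**What the plan says.** Potential Risks lists three risks: loss of privacy, skin irritation, and "risk of pneumothorax from positive pressure during cough". For the third it offers two reassurances. Central airway resistance in tracheobronchomalacia probably keeps the set pressure from reaching the distal lung, and the device maximum of 20 cm H₂O is small beside the 136–340 cm H₂O generated by coughing. It then adds: "Regardless, patients with personal history of prior pneumothorax or primary parenchymal lung disease will be excluded".

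Four items in the exclusion criteria bear on this:

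- "History of spontaneous pneumothorax"
- "Primary parenchymal lung disease"
- "History of external chest trauma"
- "Other medical conditions that interfere with participation in the study"

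No other criterion mentions pneumothorax.

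**The concern.** The risk section sets no limit on the type of pneumothorax, while the list limits it to spontaneous cases. Screening staff normally work from the list, so the narrower wording is likely to be the one applied.

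At stake is whether the protocol delivers its own safeguard. Exclusion is the only action that Potential Risks states against this risk, and the sentence is worded to apply even if the two reassurances are right. Subjects use the device at home and set the resistance themselves (Device Description). The next scheduled contact with an adverse event review is Visit 2, 11 to 28 days after the device is handed over.

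A non-spontaneous pneumothorax is also conceivable in these patients. The background section mentions intensive care admissions in severe disease, and bronchoscopy is one of the two accepted routes to diagnosis.

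**Working it through.** The point involves no sample size, power or event figure, so the check is a comparison of texts. I took each type of past pneumothorax and asked whether each section excludes it.

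| Past pneumothorax | Potential Risks | Exclusion criteria |
|---|---|---|
| Spontaneous | Excluded | Excluded by name |
| From external chest trauma | Excluded | Excluded indirectly, by the chest trauma item |
| From a procedure or mechanical ventilation | Excluded | No specific item |

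**The other half of the same sentence.** Potential Risks names two groups to exclude. Primary parenchymal lung disease appears in the list at full width. Pneumothorax appears with a qualifier that the risk section does not have. Nothing in the protocol explains the difference.

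**Whether the catch-all closes the gap.** The last exclusion, "Other medical conditions that interfere with participation in the study", is a judgement about whether a condition gets in the way of taking part. A healed pneumothorax need not interfere with about two weeks of mask use, three cough questionnaires and oscillometry. An investigator may use this item to exclude such a patient but is not required to.

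**Whether the information would be available.** The medical history at the pre-baseline visit "Should include all medically significant events prior to enrollment, including surgical procedures". A past procedure- or ventilator-related pneumothorax should come to light there, so a wider criterion could be applied with data already collected.

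**Room for more screen failures.** The Screening section says: "Up to 20 patients will be screened to achieve a total of 10 enrolled participants". This allows 20 − 10 = 10 screen failures from all causes, or 10/20 = 50% of those screened. That figure describes the room for the fix and says nothing about how common the problem is.

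**The case against.** The best reply is that the two statements do not conflict outright. The list never says that a patient with a non-spontaneous pneumothorax is eligible; it only fails to name that patient. Potential Risks is part of the same protocol and states a rule, so a reader who takes the document as a whole would exclude the wider group. This is a fair point about the label, since an investigator can follow both sections by applying the wider one. It does not remove the gap, because a reader of the list alone would apply a narrower rule.

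The remaining group is also small. Besides the trauma item, the list bars sarcoidosis, interstitial lung disease, chronic mycobacterial infection, lung cancer, lung transplantation, tracheobronchoplasty, chronic tracheal stenting and current tracheostomy. Some patients with a procedure-related pneumothorax would presumably be out on one of these grounds already. That stands, though the documents do not say how many.

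The protocol calls the risk theoretical, and nothing in it shows that a past procedure-related pneumothorax makes this device more dangerous. That stands too, and it limits the seriousness of the point. Other protections exist as well: the 20 cm H₂O ceiling, adverse event review at Visit 2 and at unscheduled visits, and the investigator's general reporting duties. None of these screens out a patient with a prior pneumothorax.

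**Conclusion.** The concern holds, as a minor one. The exclusion list delivers one of the two exclusions named in the risk section at full width and narrows the other by one word. The uncovered group is patients with a past procedure- or ventilator-related pneumothorax and no other exclusion. The list permits their enrolment but does not make it certain.

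The frequency of such histories is not given and I have not estimated it. No rise in actual risk is shown, and no endpoint or analysis is affected. The conclusion assumes only that the two sections mean what they say and that screening follows the list.

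**What to change.** Change the criterion to *History of pneumothorax (any cause)*. The documents do not show which wording was intended, but the wider one is what the risk section relies on. It needs no new visit, test or question. The one cost is that some further screened patients, possibly none, would be excluded, and they would count against the 10 screen failures the plan allows.

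If the sponsor meant to bar only spontaneous cases, the alternative is to limit the Potential Risks sentence to those cases and give the clinical reason. That would remove the inconsistency but would weaken the stated safeguard, so I prefer the wider criterion.

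### Does the loose outcome label in the Data analysis section, with no score or oscillometry index named, leave the primary result open to selection?

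*Combined protocol and SAP*

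**What the plan says.** The Objectives-primary section says the aim is to "determine if use of the nPEP device can decrease cough severity and improve cough related quality of life (QOL", which is two constructs joined by an 'and'. The Objectives-secondary section asks whether the device "improves airway physiology by decreasing proximal airway resistance as assessed by impulse oscillometry". The hypothesis under Objectives & hypothesis keeps the same structure, expecting "decreased cough severity and improve cough quality of life by decreasing proximal airway resistance".

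The Design section says that "each subject will complete validated cough questionnaires to quantify their cough severity and cough-related QOL at baseline". Description of assessments names three instruments (CQLQ, LCQ and Cough-VAS), and Study visits schedules all three at V-1, V1 and V2. The schedule table puts them in one row under a joint cough and quality-of-life heading. Nothing ranks them or says which one measures severity.

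On oscillometry, Study Interventions states: "Impulse oscillometry will be measured at V1 and 2 weeks later at V2 to assess effect of the nPEP device on airway physiology". The Description of assessments section says that the technique serves to "measure pulmonary resistance and reactance, which are graphically displayed". No frequency or index is given.

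Data analysis has three items: (a) descriptive statistics; (b) a "comparison of the primary and secondary outcomes (cough quality of life) using paired t-test", with Wilcoxon's signed-rank test as the non-parametric alternative; and (c) a before-and-after assessment of airway physiology by oscillometry, with no test named.

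**The concern.** Read literally, item (b) does not match the objectives. Its parenthesis calls both outcome tiers cough quality of life, so it drops severity from the primary outcome and gives the secondary outcome the wrong name. Item (c) then lists oscillometry without a test. With three unranked questionnaires and several possible oscillometry readouts, the measure on which each objective is judged could be chosen after the data are seen.

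What is at stake is trust in a reported improvement. Potential Benefits says the pilot will inform whether the device merits further study. There is no comparator group, so a before-and-after change is the only evidence on offer, and picking the most favourable score would inflate it.

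**Working it through.** **Text comparison**

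| Element | Objectives | Data analysis | Left open |
|---|---|---|---|
| Primary | Severity and quality of life | (b), glossed as quality of life; paired t-test or signed-rank | Which score stands for which construct |
| Secondary | Lower proximal resistance by oscillometry | Within (b) by tier, in (c) by name | The index, and whether (b) supplies the test |

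Item (b) claims to cover the primary and secondary outcomes, and the objectives define what those are. On that reading the paired test already applies to severity, quality of life and resistance, and the parenthesis is shorthand for the questionnaire battery, much as in the schedule table. The secondary objective also fixes the construct (proximal resistance) and the direction (a decrease), so reactance is not a candidate for that outcome.

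**Inputs**

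- From the documents: ten subjects (Design), three questionnaires (Description of assessments), paired t-test or signed-rank test (Data analysis).
- Assumed, because the documents give no value: two-sided alpha 0.05, normal paired differences, no true effect, and a common correlation r of 0, 0.5 or 0.8 between the three change scores.
- The plan states no alpha, power or effect size, so there is no figure of its own to reproduce.

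**One named score.** The false favourable rate is 0.05/2 = 2.5%.

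**Any of three favourable.** At r = 0: 1 − 0.975³ = 1 − 0.9269 = 7.3%. Simulated paired t-tests with n = 10 give 6.4% at r = 0.5 and 5.1% at r = 0.8.

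**Severity and quality of life both favourable,** with one score for severity and either of the other two for quality of life. At r = 0: 0.025 × (1 − 0.975²) = 0.025 × 0.0494 = 0.12%. Simulation gives 0.7% at r = 0.5 and 1.4% at r = 0.8.

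**Apparent gain from reporting only the best of three.** The expected maximum of three mean differences, in SDs of the paired difference, is (1.5/√π) × √(1 − r)/√10:

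- r = 0: 0.846 × 1/3.162 = 0.27
- r = 0.5: 0.846 × 0.707/3.162 = 0.19
- r = 0.8: 0.846 × 0.447/3.162 = 0.12

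The 95% confidence interval half-width at n = 10 is t(0.975, 9)/√10 = 2.262/3.162 = 0.72 SD. The gains are therefore 37%, 26% and 17% of that half-width.

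| Success rule | r = 0 | r = 0.5 | r = 0.8 |
|---|---|---|---|
| One named score | 2.5% | 2.5% | 2.5% |
| Any of three | 7.3% | 6.4% | 5.1% |
| Severity and quality of life both | 0.1% | 0.7% | 1.4% |

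Three cough scores from the same patients are likely to be correlated, so the right-hand columns are the more relevant. The inflation depends wholly on the 'any of three' rule, or on discarding the two weaker scores. The plan directs neither.

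**The case for a change.** The strongest case for a change is that naming scores in advance costs one paragraph and needs no new data, visits or subjects. The documents separate severity from quality of life in several places, so the parenthesis in (b) does not match them. The plan proposes hypothesis tests, has no control group, and nowhere promises to report all three questionnaires. A pilot used to decide on further work is more convincing when its measure is fixed beforehand.

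Much of this stands as a matter of drafting. The label is loose, no score is mapped to severity, and no oscillometry index is named. A report that showed only one of the three scores would deserve questioning.

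It does not show that the planned analysis is wrong. Every candidate cough score is listed, collected at V1 and V2, and covered by a stated test, so selective reporting would be a departure in the write-up and not something the plan leads to. The obvious remedy of a single primary score would also demote one of the two constructs that the primary objective puts on an equal footing, which narrows the objective and does not merely clarify it. For oscillometry, the construct and direction are already set, and the same paired comparison is the natural reading.

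**Conclusion.** No change to the plan follows. This is a gap in specification, together with a loosely worded parenthesis, that an analyst fills sensibly: paired comparisons from V1 to V2 on all three questionnaires and on oscillometric proximal resistance, all reported.

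The worst case, in which any one favourable score counts, raises a false favourable result from 2.5% to between 5.1% and 7.3%. The objective as worded, with severity and quality of life both required, puts it at 1.4% or less. These figures rest on an assumed two-sided 0.05, normal differences, no true effect and correlations from 0 to 0.8. The plan sets no alpha and no success rule, so no stated error rate is breached. No size can be given for the choice of oscillometry index, because the documents do not list the indices to be recorded. In a ten-subject uncontrolled pilot, whose result can only suggest whether to study the device further, the ambiguity does not alter what will be measured or which tests will be run on the cough scores.
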